3.4.3 Individual Unblinding for Clinical Emergencies

If there is an urgent clinical requirement to know a subject's treatment assignment, the investigator (in consultation with the medical monitor, if possible) will make a written request to the investigational pharmacist or product manager for urgent unblinding of a subject's treatment. The request must include the subject ID number, the date, a brief justification of the clinical requirement to the Study Drug manager in the research pharmacy, and the investigator's signature. The request will be kept in the study file.

Upon receipt of proper written request, the investigational pharmacist or product manager will disclose the treatment group to the investigator. The sponsor must be notified immediately of any clinically required break of the study blind on an Immediately Reportable Event Form.

3.5 Clinical Evaluation, Photography, Decontamination and Treatment of Wounds

The correct management of rabies bite wounds in animals has as much influence on the development of rabies as vaccination and wound immunoglobulins (Dean et al. 1963). Regardless of the risk for rabies, the optimal medical treatment of animal bite wounds includes the evaluation and treatment of serious nerve, tendon and vascular lacerations. Avoidance of infection through wound debridement and irrigation will yield the best possible cosmetic results. Care should be taken not to damage skin or tissues (Manning et al. 2008). Immediate gentle irrigation with at least 200 mL of sterile water or normal saline with either commercially available wound cleansing solutions, mild soap or povidone-iodine (10%) diluted to 1-2% concentration in water. Gentle cleaning of the wound with gauze may be required. Irrigation should involve gentle cleaning with irrigation fluid expressed through 20 to 21 gauge plastic catheter tip from a 30 to 50 mL syringe. The tip of the catheter should be held approximately 2 cm from the wound surface. (Gouin et al. 2001, Singer et al. 2008). Eye protection and splash guards should be employed for protection of medical staff. Puncture wounds should be gently cleaned with cotton swabs and irrigation solution. Wound cleansing is especially important in rabies prevention because wound cleansing alone without other PEP markedly reduces the likelihood of rabies in animal studies (Kaplan et al. 1962, Dean et al. 1963).

Local anesthetics may be employed to assist in wound management.

Complete primary wound closure should be avoided with delayed closure employed when necessary. Partial closure may be individualized on the basis of wound size and location of the wound(s), and time interval since the bite with delayed closure at a later time. Suturing should be avoided when possible. When wounds require some closure (such as suturing) this should occur only after administration of Study Drug.

Decisions regarding the use of antibiotic prophylaxis and management of infection (both local and systemic) should be individualized based on the wound and the biting animal.

If the subject has received the primary tetanus immunization series and has not received a tetanus booster within 10 years (or five years for severely contaminated bite wound) a tetanus vaccine booster immunization should be given. Tetanus immunization should be begun if the subject has not received a primary tetanus vaccination series.

Uncalibrated photographs of all wounds should be recorded if possible within 48 hours of PEP start. The photograph should record the date and the subject number but no other personal identification. The photos with facial characteristics should be pixelated before permanent storage to avoid identification. All photos will be stored in a locked secure location at the research site and if stored electronically should be encrypted and access limited by an access roster. The photographs are for medical use only and may not be used commercially.

3.6 Decontamination of Mucous Membranes

Mucous membranes of the eyes nose and mouth may be decontaminated by copious irrigation with potable water or sterile saline.

3.7 Study Drug Infiltration for Bite and Non-bite Exposures

After decontamination and before wound dressing the wound surface itself should be injected with the calculated dose of Study Drug through a 25 gauge needle or similar of approximately 2.5 to 3 cm in length. Study drug should be injected through the skin subcutaneously as if local anesthesia were being administered creating a wheal of fluid within a centimeter of the wound margin. After creation of the first wheal the needle should be withdrawn with the tip remaining in the injection hole and the needle redirected to accomplish infiltration of a different axis. If the wound involves muscle tissue, injection of the muscle should be performed. If the wound surface has been thoroughly injected and there is remaining Study Drug it should be injected subcutaneously as close to the wound as anatomically possible.

Care should be taken to avoid intravenous or intra-arterial injection by aspiration and looking for blood return before infiltration. Remove the needle and re-insert it in a new location and repeat the aspiration step before administering. All bite injuries and breaks in the skin related to bites should be infiltrated with Study Drug. Infiltration of finger compartments or other anatomic

compartments should be done with a volume appropriate to the anatomic volume to avoid compartment syndrome. Study drug should be administered within 45 minutes of when the dose is constituted. Study drug volume may be expanded with dilution of normal saline if the extent of the wound area to be injected is large and may require extra injection volume. All Study Drug must be injected. Subjects must be observed for at least 60 minutes after the end of Study Drug administration.

For the non-bite exposures the calculated doses of Study drug should be administered intramuscularly as above without regard to proximity to exposure.

3.7.1 Human Rabies Immune Globulin (HyperRab® S/D)

There are two dosage forms of HRIG that may be used in the study a presently available 150 IU/mL preparation and a newly available 300 IU/mL preparation. All stocks of 150 IU/mL HRIG (HyperRab) should be used at a study site before the study site can switch to the 300 IU/mL preparation. Once a study site has switched to the 300 IU/mL preparation it cannot again use the 150 IU/mL.

The dose of HRIG (HyperRab) 20 IU/kg should be calculated based on body weight. The dose for the 150 IU/mL potency preparation is 0.133 mL/kg. The dose for the 300 IU/mL potency is 0.0665 mL/kg.

The calculated dose should be administered into the wound whether in subcutaneous tissue or muscle. For example, a 70 kg person receiving the 150 IU/mL potency has a calculated dose of 9.31 mL. The entire calculated dose must be given. If the fluid volume of the injection needs to be increased to enable all sites to be injected the pharmacy may dilute the calculated dose with saline when the syringe is prepared. Doses up to 3 mL may be given in at a single injection site (Hopkins et al. 2013).

Care must be taken NOT to administer a rabies vaccine near the Study Drug administration site.

3.7.2 SYN023

After thorough wound sanitation, injections of the entire calculated dose of SYN023 should be administered into and around all the bite wounds on Study Day 1. The dose of SYN023 should be calculated based on body weight: 0.3 mg/kg. For example, a 70 kg person has a calculated dose of 21 mg. The entire calculated dose should be given. Doses up to 3 mL may be given at a single injection site. Care must be taken NOT to administer a rabies vaccine near the Study Drug administration site.

3.8 Rabies Vaccine (RabAvert® or Rabipur®) Administration

Rabies Vaccine (RabAvert® or Rabipur®) must be administered in a different area from the Study Drug infiltration to reduce interference. The 1 mL dose of the chicken fibroblast rabies vaccine should be administered in deltoid muscle. If not possible, then vaccination may be administered in the vastus lateralis (thigh) or rectus femoris (thigh). Five doses of the rabies vaccine should be administered on Study Days 1, 4, 8, 15 and 29. The rabies vaccine should be administered as soon as possible after dose constitution. Rabies vaccination should be administered within 75 minutes after Study Drug.

3.9 Study Efficacy Evaluations

3.9.1 Clinical Efficacy Evaluations

The absence of a confirmed or probable case of rabies in the per-protocol population is part of the composite endpoint. Subject will be periodically evaluated for the clinical signs and symptoms of human rabies. If these develop they will be referred for medical evaluation and laboratory or anatomic confirmation. All clinical rabies diagnostic tests may be performed locally at a qualified laboratory. All rabies cases will be reviewed by the DSMB.

Human Rabies Clinical Case Definition:

A person presenting with an acute neurological syndrome (encephalitis) dominated by forms of hyperactivity (furious rabies) or paralytic syndromes (dumb rabies) progressing towards coma and death, usually by respiratory failure, within 7-10 days after the first symptom if no intensive care is instituted.

A subject who is alive and not hospitalized is presumed not to have rabies. Contact with a non-hospitalized subject on any date is evidence that rabies has not occurred on that date. If a subject is discharged from hospital rabies has not occurred.

Case Classification Human Rabies

- Suspected: A case that is compatible with the clinical case definition
- Probable: A suspected case (above) plus history of contact with a suspected rabid animal.
- Confirmed: A suspected case that is laboratory-confirmed.

Rabies Laboratory Diagnosis Confirmation Criteria

One or more of the following:

- Rabies viral isolation from clinical specimens
- RVNA in the CSF
- Detection of rabies viral RNA by RT/PCR in clinical specimens, saliva,
- Detection of rabies by FAT on skin biopsy such as from neck (ante mortem).
- Detection of rabies by FAT preferably brain tissue (collected post mortem).

- Detection of rabies by FAT after inoculation of brain tissue, saliva or CSF in cell culture, or after intracerebral inoculation in mice or in suckling mice.
- Detection of viral nucleic acids by PCR on tissue collected before or after death in a clinical specimen (brain tissue or skin, cornea, urine, saliva or other).

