- In Synermore's experience about 2% to 5% of subjects may have evidence of unknown or unrecalled rabies vaccination. Their RVNA response may be much quicker and higher than in naïve patients. Since the RVNA is a crucial efficacy element these subjects with a RVNA ≥ 0.1 IU that is taken to be evidence of previous vaccination must be analyzed differently.
- Subjects will be excluded for conditions discovered after randomization that impair protection such as immunodeficiency.
- Subjects will be excluded if excessive treatment delay (>54 hours) is discovered.
- Subjects will be excluded if they receive or have received protocol prohibited treatments such as RIG that will confound analysis.
- Subjects will be excluded if all of the bite wounds are discovered to have not been properly treated or injected.
- Subjects will be excluded if bites are determined to be due to non-protocol listed animals
- Subjects will be excluded if they leave the trial or their status is unknown.

Rationale for bite, broken skin lick and broken skin scratch exposure injuries eligibility for trial
Individuals with WHO Category III rabies exposures with some exceptions are eligible for the trial since they are considered WHO Category 3 exposures and RIG is indicated for these exposures. WHO Category 3 exposures include single or multiple transdermal bites or scratches or licks on broken skin, mucous membrane saliva contamination and unprotected bat exposures. Depending on the protocol defined risk substratum all observed bites, broken skin scratches and broken skin licks unprotected bat contacts and saliva contamination of mouth nose and eyes are eligible for the trial.

Rationale for bite-to-treatment interval

The bite-to-treatment interval for the administration of RIG is recommended to be as soon as possible up to 7 days by the WHO (WHO 2013). This judgment reflects the emergence of naturally produced antibodies at about 7 days. A number of surveys report that rabies cases were rare when treatment was instituted within 2 to 3 days (Si et al. 2008, Quiambao et al. 2009).

Animal studies suggest that rabies virus may enter nerves within hours (Watson et al. 1981).

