3.2.6 Major Protocol Deviations and Eligibility for the Per-protocol Population

Continuation in the per-protocol population depends on the absence of uncorrectable major protocol deviations. Major deviations are those that would degrade the fidelity of the data from the protocol. Protocol deviations requiring removal from the per-protocol population include but are not limited to those listed below.

- Defective informed consent
- Received the incorrect Study Drug
- Received the incorrect dose ($\pm 20\%$) of Study Drug
- Failed to complete the scheduled rabies vaccinations through Study Day 29
- Are discovered to lack adequate prophylactic treatment of all exposure sites
- Are discovered to be injured by animal other than those listed
- Are discovered to have an interval > 54 hours from rabies exposure to the start of prophylaxis
- Are discovered to have RVNA ≥ 0.1 IU in serum obtained at Study Day 1
- Receives prohibited treatment during the trial
- Are found not to have a modified WHO Category 3 exposure (Table 2.2-1, Section 3.9.4)
- Are discovered to have or have developed HIV infection or other immunodeficiency state.
- Second high risk animal bite or contact requiring PEP

Subjects who are discovered to not have satisfied any criteria for the per-protocol population may be excluded from that population (Section 3.2.8). These deviations may become known at different intervals from randomization. Likely intervals for discovery of these deviations are listed in Table 3.2.6-1 based on the occurrence of site review, monitoring visits and vaccination schedules.

Table 3.2.6-1 Intervals for Per-protocol Exclusions (approximate)

Major Protocol Deviation	Rationale	Likely Interval Days
Defective consent	Data without effective consent cannot be used	43
Diagnosis of HIV after enrollment	New HIV may affect PEP response	365
Received incorrect study drug	Mixes SYN023 and HIRG results	43
Incorrect dose ($\pm 20\%$) of Study Drug	Arbitrary but reasonable dose margin. Used for biosimilars.	43
> 54 hr from rabies exposure to the Study Drug	Early PEP initiation is important Should be discovered early from wound state and investigation	15
Failed to complete all rabies vaccinations	Important feature of PEP. Should be known by Study Day 29	29

Failure to treat all exposure sites	Documented cause of treatment failure. Should be discovered early from wound state and investigation	15

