3.12.4 Concomitant Medications and Prohibited Medications

The collection of information on concomitant medications used by subjects following Study Drug administration will coincide with the collection period of adverse events. The collection period for concomitant medications associated with the treatment of adverse events will be 42 days following the last Study Drug. The collection period for concomitant medications associated with the treatment of serious adverse events (SAE) will be Study Days 1-365. The collection period for prohibited medications will be Study Days 1-365.

Concomitant medication includes prescription and non-prescription drugs or other treatments, and any vaccines other than rabies or tetanus vaccines specified by the protocol. The name of the medication, treatment start and stop dates (or 'ongoing'), route of administration, and indication must be recorded on the Concomitant Medications case report form (CRF). The indication recorded on the Concomitant Medications CRF must correspond to a medical term/diagnosis recorded on the adverse event (AE) CRF, or to a pre-existing condition noted in the subject's medical history, or be noted as prophylaxis, e.g., dietary supplement.

Prohibited medications include any vaccination or immunoglobulin directed against rabies. Systemic corticosteroids or other immunosuppressants administered within 29 days of first rabies vaccination are prohibited.

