5.1.5 Data and Safety Monitoring Committee (DSMB)

The study will have a DSMB composed of a physician chairman/chairwoman, three member physicians and a DSMB statistician all of which may vote. At least one physician should be an Infectious Disease or rabies expert. The voting members will not be directly involved with the conduct of the study. Voting members will not be employees of the sponsor. Additional non-voting subject area experts may be present at meeting to provide expertise if requested by the DSMB. The DSMB will operate according to its charter.

The DSMB will have five responsibilities

1. Review of Study Drug pharmacodynamic activity in the Initial Enrollment of the LRG subjects and granting permission for general LRG enrollment (5.1.5.2).
2. Review of safety and pharmacodynamics through Study Day 99 in the initial and general enrollment groups of the LRG (5.1.5.3)
3. Review of Study Drug safety after 80 subjects have reached Study Day 9 (5.1.5.4)
4. Review and confirmation of any possible rabies cases in trial participants.
5. Management of safety issues during the trial.

The DSMB will not determine exclusions from the per protocol population. Exclusions from the per protocol population are determined by the Per Protocol Adjudication Board. The DSMB may request review of any case by this board.

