5.1.5.1 DSMB Confirmation of Rabies Cases in the Trial

A confirmed or probable case of rabies is an element of the composite endpoint for the trial (Section 3.9.1). If a case of rabies occurs in the SYN023 treatment group of the per protocol population in the trial it will result in the failure of the primary objective and the cessation of Study Drug administration in the trial. The DSMB will review and confirm a rabies diagnosis in any study participant and determine if trial enrollment or Study Drug administration should be stopped. The DSMB may require additional subjects in the Initial Enrollment.

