4.3. Analysis Set

The Per-protocol Adjudication Board will review blinded data and decide whether to exclude a subject from the Per-protocol Populations before each DSMB meeting. All analysis set definitions should be finalized prior to final study unblinding or through thorough review in the Blinded Data Review Meeting (BDRM). The list of major protocol deviations must be finalized prior to the database lock and unblinding.

Primary analyses will be performed on the Per-protocol Populations. The As-treated Population will be applied on the primary endpoints as sensitivity analyses.

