5.2. Protocol Deviations

All protocol deviations (including violations) will be assessed and reviewed at the BDRM prior to the database lock. Any exclusion of randomized subjects from the Per-protocol Population after randomization must be made by the Per-protocol Adjudication Board. Subjects with the following significant deviations will be excluded from the Per-protocol Populations:

- Defective informed consent
- Received the incorrect study drug
- Received the incorrect dose ($\pm 20\%$) of study drug
- Failed to complete the scheduled rabies vaccinations through Study Day 29
- Are discovered to lack adequate prophylactic treatment of all exposure sites
- Are discovered to be injured by animal other than those listed
- Are discovered to have an interval >54 hours from rabies exposure to the start of prophylaxis
- Are discovered to have RVNA ≥ 0.1 IU in serum obtained at Study Day 1
- Receive prohibited treatment during the trial
- Are found not to have a modified WHO Category 3 exposure
- Are discovered to have or have developed HIV infection or other immunodeficiency state
- Second high-risk animal bite or contact requiring PEP

As the study is ongoing, additional significant protocol deviations can also be identified or defined by the Per-protocol Adjudication Board. The list of significant protocol deviations can be updated accordingly.

Significant deviations categorized according to the list will be summarized in a table for the As-treated Population. All protocol deviations will be presented in a listing and an additional listing

of deviations for the randomized subjects who missed any dose of study drug or rabies vaccine will be provided.

6. Demographics and Baseline Characteristics

Demographic parameters (age, gender, race and ethnicity), randomization factors (including study site and bite location) and other baseline characteristics will be summarized by treatment group for all subjects in the As-treated Population. The summary can be used to check potential imbalance between treatment groups.

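### Element 4 (no rabies) is decided on the per-protocol set, and no rule keeps a case in the count if its exclusion is first raised after suspected rabies is known; the one-case figures in protocol 7.8.5 also do not fit 184 subjects

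*Protocol*

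**What the plan says.** **Where element 4 is decided.** Protocol 3.9.1: "The absence of a confirmed or probable case of rabies in the per-protocol population is part of the composite endpoint". Protocol 5.1.5.1 says that if a case occurs in the SYN023 arm of the per-protocol population, "it will result in the failure of the primary objective and the cessation of Study Drug administration in the trial". SAP 8.1 performs the primary efficacy analyses on the NRG per-protocol population. SAP 8.1.2 repeats all four elements on the as-treated population, as sensitivity analyses only.

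**Who decides membership, and when.** SAP 4.3: "The Per-protocol Adjudication Board will review blinded data and decide whether to exclude a subject from the Per-protocol Populations before each DSMB meeting". The same section has analysis sets settled before final unblinding. Protocol 3.2.8 says the Board sees blinded data and cannot unblind. It may exclude a subject after weighing the deviation's effect on the data.

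**On what grounds.** Protocol 3.2.6: "Protocol deviations requiring removal from the per-protocol population include but are not limited to those listed below". SAP 5.2 adds that, while the study is ongoing, "additional significant protocol deviations can also be identified or defined by the Per-protocol Adjudication Board". Protocol 5.1.5 says of the DSMB: "The DSMB may request review of any case by this board".

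**One-case figures.** For one case among the 184 SYN023 subjects of the NRG, protocol 7.8.5 gives 0.6% with a 95% CI of 0% to 2.0%. Protocol 7.3 gives 0.63% with 0 to 2% on 160. Protocol 7.8.5 and SAP 8.1.1.4 both call the chance of a case small.

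**The concern.** Element 4 is the only clinical outcome in the composite, and its criterion is zero cases, so one subject's set membership can decide the primary objective. The Board's blinding covers treatment. No passage extends it to rabies status or says that membership is fixed once rabies is suspected.

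The sponsor's own expectation makes this more than a formality. Protocol 7.8.5 says any case would more likely come from failures of clinical management or of protocol procedures. Several exclusion grounds in 3.2.6 are failures of that kind; Table 3.2.6-1 describes failure to treat all exposure sites as a known cause of treatment failure. Investigating a case would therefore mean looking for the deviations that could remove it from the deciding set. A pass on element 4 reached that way would be open to challenge, even if the exclusion were sound.

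**Working it through.** **1. Reading the passages together.**
- A suspected case pauses dosing for DSMB review (protocol 6.1.2).
- The Board rules on exclusions before each DSMB meeting (SAP 4.3), and the DSMB may refer any case to it (protocol 5.1.5).
- Table 3.2.6-1 expects most procedural deviations to surface by about Day 15 to 43, but lists HIV, prohibited treatment and a second exposure at Day 365. Deviations defined by the Board have no time limit before analysis sets are settled.
- Protocol 1.6 puts most incubations at 46 to 189 days.

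Most exclusions should therefore precede onset, but the text allows some to follow it.

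**2. The plan's one-case figures.** Rate = 1/n. Wald limits = p ± 1.96 × √(p(1 − p)/n). The exact (Clopper-Pearson) limits for one event solve 1 − (1 − p)^n = 0.025 (lower) and (1 − p)^n + np(1 − p)^(n−1) = 0.025 (upper).

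| | Rate | Wald upper limit | Exact 95% CI | Plan states |
|---|---|---|---|---|
| 1/160 (protocol 7.3) | 0.625% | 1.85% | 0.02% to 3.43% | 0.63%, 0 to 2% |
| 1/184 (protocol 7.8.5) | 0.54% | 1.61% | 0.01% to 2.99% | 0.6%, 0% to 2.0% |

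Section 7.3 reproduces on 160 as a rounded Wald interval cut off at zero, a method unsuited to a single event. Section 7.8.5 does not reproduce on 184: the rate rounds to 0.5%, and neither upper limit is 2.0%. It appears to carry the 160-subject figures.

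**3. Chance of at least one case.** 1 − (1 − r)^n, with the sponsor's r of 0.01% to 0.1% (protocol 7.8.5):
- n = 184: 1 − 0.9999^184 = 1.8%; 1 − 0.999^184 = 16.8%.
- n = 160: 1.6% and 14.8%.

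**4. How often the choice of set decides element 4.** Per arm, 184 − 160 = 24 SYN023 subjects are planned to fall outside the per-protocol set. The probability of a case among those 24 and none in the 160 is [1 − (1 − r)^24] × (1 − r)^160:
- r = 0.01%: 0.00240 × 0.984 = 0.24%.
- r = 0.1%: 0.0237 × 0.852 = 2.0%.

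This treats exclusion as unrelated to rabies. On that footing it is an upper bound on the mechanism at these rates, because it includes subjects properly excluded before onset. The 24 also cover loss to follow-up. If an exclusion were prompted by the case itself, the formula would not apply. The documents give no figure for that, and step 3 (n = 184) then gives only the chance that the question arises at all.

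**The case against.** The strongest defence is that the Board cannot see treatment, so it cannot knowingly favour SYN023. Its judgments go to the DSMB and its reasons are recorded (protocol 3.2.8). The DSMB reviews any rabies diagnosis in any participant (5.1.5.1). The as-treated analysis covers element 4 (SAP 8.1.2), and SAP 8.2 reports cases in subjects given SYN023 within 54 hours. All of this stands, and it means a case would not be hidden. It does not alter the formal pass or fail, which rests on the per-protocol count.

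A second defence is that element 4 is meant to measure failure in properly treated subjects (protocol 1.6 and 7.3), so excluding an inadequately treated case is legitimate. That also stands. It is the real cost of the remedy and a reason to write the rule before any case occurs.

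Four stronger readings are tempting but not supported:
- **Treatment for rabies triggers removal.** Protocol 3.12.4 says "Prohibited medications include any vaccination or immunoglobulin directed against rabies", and prohibited treatment is a ground for removal. But no passage describes giving either product to a suspected case.
- **Unknown status removes a case.** Protocol 1.6 says "Subjects will be excluded if they leave the trial or their status is unknown", but a subject with known suspected rabies does not have unknown status on that point.
- **The stated intervals exaggerate the evidence from one case.** They lie lower than the exact ones and include zero, so they do not. They also already contain the sponsor's 0.1%.
- **The population for element 4 is undefined.** The objective says only SYN023 recipients, but protocol 2.2.1 and 5.1.5.1 and SAP 8.1 settle it. The gap is editorial.

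**Conclusion.** The point holds. Nothing in the documents prevents an exclusion first raised after suspected rabies is known from removing the case that decides element 4. If the other elements passed, that would turn a failed primary objective into a met one. This is a gap in the rules; the documents do not suggest that anyone intends to use it.

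The probability is small: at most 0.24% to 2.0%, given the sponsor's failure rates, 24 subjects outside the set, and exclusion unrelated to rabies. The consequence is large, because the criterion is zero cases.

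The figures in protocol 7.8.5 are wrong for 184 subjects. Section 7.3 is arithmetically reproducible but uses a poor interval. Neither correction changes the one-case rule.

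**What to change.** **(a) Rule on exclusions.** In protocol 3.2.8 and SAP 4.3 and 5.2, state that Board decisions are made masked to rabies status. Because a suspected case pauses dosing and masking may fail, also state that, for element 4 only, an exclusion first raised after onset of suspected rabies does not remove the case from the count. Report NRG per-protocol and NRG as-treated SYN023 case counts side by side, with the Board's reasons and dates.

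**(b) Figures.** In protocol 7.8.5 give 0.54% (exact 95% CI 0.01% to 2.99%) for 1/184. In 7.3 give 0.63% (0.02% to 3.43%) for 1/160. Name the method in both. In 7.8.5 and SAP 8.1.1.4, replace the small-chance wording with a chance of about 1.8% to 16.8% of at least one case at n = 184 under the sponsor's rates.

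**(c) Editorial.** Name the NRG per-protocol population in the element 4 wording of the objective (protocol abstract and 2.1; SAP 2.1). Protocol 5.1.5.1 refers to a case of rabies, whereas protocol 6.1.2 and SAP 8.1.1.4 refer to a confirmed case when describing the stop; the sponsor must reconcile these passages.

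**Cost.** The changes are to wording only, and the as-treated summary is already planned. The downside is that a case with a genuine deviation found late, even one that explains the failure, would count against SYN023. The side-by-side counts and recorded reasons let readers judge that.
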